4. STUDY DESIGN

4.1 Overall Study Design

This is an open-label, phase I study of lenalidomide in after allo-HCT in AML and MDS subjects with MRD detected by the CD34+ mixed chimerism analysis. The study is designed to evaluate the safety profile, maximum tolerated dose and biologic activity of lenalidomide in patients with AML and MDS after allo-HCT. Subjects will be recruited in cohorts of 3. Each subject will receive lenalidomide daily for 21 days per cycle for 2 cycles (42 days). Duration of each cycle is 28 days. The starting dose will be 2.5 mg given orally every other day. Subjects will be evaluated for DLTs from the first dose and until 14 days after the last dose of lenalidomide.

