4.2 Dose Escalation

The dose levels of lenalidomide will be as follows:

- Dose Level 1: 2.5 mg PO QOD Day 1-21 for 28-day cycle X 2 cycles
- Dose Level 2: 2.5 mg PO QD Day 1-21 for 28-day cycle X 2 cycles
- Dose Level 3: 5 mg PO QD Day 1-21 for 28-day cycle X 2 cycles
- Dose Level 4: 7.5 mg PO QD Day 1-21 for 28-day cycle X 2 cycles

The dose escalation phase of the study will utilize a standard “3 + 3” design to estimate the MTD for lenalidomide. A description of the statistical characteristics (probabilities of halting or continuing dose escalation) of this design is provided in Appendix G: Statistical Characteristics of the “3+3” Design. For this study, MTD will be defined as the highest dose at which no more than 34% of the subjects observed at a given dose level experience a DLT. Subjects will be individually assessed for safety and DLTs for the purpose of determining the MTD. Three eligible subjects will be enrolled in sequential cohorts at increasing dose levels until at least one (1) DLT is seen between the first dose and 14 days after the last dose of lenalidomide. The following dose escalation rules will be used and applied:

1. Three subjects are initially studied at each dose level.
2. If none of these 3 subjects experience DLT, then the dose is escalated to the next dose level in 3 subsequent subjects.
3. If 1 of these 3 subjects experiences DLT at the current dose, then up to 3 more subjects are recruited at the same dose level.
 - a) If none of these 3 additional subjects experience DLT, then the dose is escalated to the next dose level in 3 subsequent subjects.
 - b) If 1 or more of these 3 additional subjects experiences DLT, then the MTD is considered to have been exceeded and the previous dose level will be the MTD.
4. If 2 or more of the initial 3 subjects at a dose level experience DLT, then the MTD is considered to have been exceeded and dose escalation will be stopped. Up to 3 more subjects are treated at the next lower dose.

A subject must meet one of the following 3 criteria to be evaluable for dose-escalation decisions:

[figure not shown]
1. Completed at least 21 days of lenalidomide without a DLT by 14 days after the last dose of lenalidomide;

2. Experienced a DLT between the first dose and 14 days after the last dose of lenalidomide; or
3. Withdrawn from the study after at least 14 days of lenalidomide administration.

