10.2 Period of Observation

For the purpose of this study, the period of observation for adverse events starts on the day the subject signs informed consent. For subjects who fail screening, the period of observation ends on the date of screening failure. Treated subjects, including those who were prematurely discontinued from the study, will be followed for any adverse events that occur during the study from the time the subject signs the informed consent form until 28 days (\pm 2 days) following the last dose of study treatment (*i.e.*, the Follow-up Visit). However, if another course of anti-cancer therapy is initiated prior to the 28-day follow-up period visit, collection of adverse events will no longer be performed, with the exception of events that may be possibly, probably, or definitely related to the investigational agent or are clinically significant.

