11. DISCONTINUATIONS

11.1 Discontinuation of Subjects

A subject must be discontinued from protocol-prescribed therapy under the following circumstances:

- Consent withdrawal at the subject's own request or at the request of their legally authorized representative;
- Unacceptable toxicity or adverse event as determined by the Principal Investigator and/or subject;
- Significant deviation from inclusion/exclusion criteria, in the opinion of the Principal Investigator;
- If, in the Principal Investigator's opinion, continuation in the study could be detrimental to the subject's well-being;
- Relapsed or progressive disease;
- Initiation of chemotherapy for relapsed or progressive disease.

If a female subject or the female partner of a male subject who is required to use defined contraceptive methods becomes pregnant after the study, the female subject or pregnant partner must be followed until the outcome of the pregnancy is known.

As far as possible, all end-of-study examinations must be performed on all subjects who receive the study drug but do not complete the study according to protocol. All subjects who discontinue from protocol-prescribed therapy for any of the reasons above will be followed for a period of 30 days following the last day of study drug administration.

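### Evaluability criterion 3 does not require that the DLT window was observed, so a subject lost after 14 days of drug can be counted as a non-DLT

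*Combined protocol and SAP*

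**What the plan says.** **DLT window.** Section 4.1: "Subjects will be evaluated for DLTs from the first dose and until 14 days after the last dose of lenalidomide".

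**Evaluability for escalation decisions.** Section 4.2 lists three alternatives, and the Synopsis has the same list.
- Criterion 1: "Completed at least 21 days of lenalidomide without a DLT by 14 days after the last dose of lenalidomide".
- Criterion 2: a DLT between the first dose and 14 days after the last.
- Criterion 3: "Withdrawn from the study after at least 14 days of lenalidomide administration".

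The first two refer to the DLT window; the third does not. The Synopsis adds that a subject who meets none of the three is replaced.

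**Use of the count.** Section 4.2: "If none of these 3 subjects experience DLT, then the dose is escalated to the next dose level in 3 subsequent subjects"; and "If 1 of these 3 subjects experiences DLT at the current dose, then up to 3 more subjects are recruited at the same dose level". Escalation follows if none of the added three has a DLT.

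**Follow-up after stopping.** Section 10.2: "Treated subjects, including those who were prematurely discontinued from the study, will be followed for any adverse events that occur during the study", up to 28 days after the last dose. Section 11.1 says that subjects who discontinue therapy "will be followed for a period of 30 days following the last day of study drug administration".

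**Other rules on who counts.** Section 11.2 replaces anyone withdrawn before completing 21 days of drug, whatever the reason. Section 13.2.2 accepts five doses without a DLT and sets no window condition.

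**The concern.** The escalation rules have only two outcomes for an evaluable subject: DLT or no DLT. A subject who is evaluable under criterion 3 and has no recorded DLT counts as a non-DLT, whether or not anyone looked for one through the end of the window.

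Beyond criteria 1 and 2, criterion 3 admits two groups:
- subjects with 14 to 20 days of drug and no DLT seen;
- subjects with 21 or more days of drug who were withdrawn before the window closed. They miss criterion 1 only because the window was not completed, and criterion 3 lets them back in.

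The MTD is part of the primary objective and rests on three to six subjects per level, so one subject can decide a cohort. Compared with full observation of the same subject, an unseen DLT can only lower the count. The error therefore runs one way, towards escalation and a higher declared MTD.

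**Working it through.** **1. Inputs from the plan.** The 3+3 rules are in section 4.2. Two 28-day cycles with drug on days 1 to 21 put the last planned dose on Day 28 + 21 = 49. The DLT window of a full-course subject then closes on Day 49 + 14 = 63. For a subject who stops at Day 14 it closes on Day 14 + 14 = 28.

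**2. Assumptions not in the plan.** DLT hazard is constant over the 63 days, withdrawal is independent of DLT, and exactly one of the first three subjects stops early.

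**3. Reproduce Appendix G.** With true DLT probability p and q = 1 − p:

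P(escalate) = q³ + 3pq² × q³

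At p = 0.33: 0.3008 + 0.4444 × 0.3008 = 0.434, against 0.43 in Appendix G. All ten columns agree to rounding. The table is correct for subjects observed over the whole window; it does not model partly observed ones.

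**4. One early stopper among the first three.** The chance that a subject observed for t days shows a DLT is p_t = 1 − q^(t/63). Then:

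- P(0 of 3) = q²(1 − p_t)
- P(1 of 3) = 2pq(1 − p_t) + q²p_t
- P(escalate) = P(0 of 3) + P(1 of 3) × q³

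At p = 0.33:
- Lost at Day 14: p_t = 0.085; 0.4107 + 0.4428 × 0.3008 = 0.544.
- Observed to Day 28: p_t = 0.163; 0.3757 + 0.4433 × 0.3008 = 0.509.

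| True DLT rate | Lost at Day 14 | Observed to Day 28 | Replaced, fully observed |
|---|---|---|---|
| 0.33 | 0.544 | 0.509 | 0.434 |
| 0.40 | 0.422 | 0.385 | 0.309 |
| 0.50 | 0.272 | 0.238 | 0.172 |

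**5. Split the rise.** At 0.33 the total is 0.544 − 0.434 = 0.110. Missing observation accounts for 0.544 − 0.509 = 0.035, about a third. Shortened exposure accounts for 0.509 − 0.434 = 0.075. The observation share is also about a third at 0.40 (0.037 of 0.113) and at 0.50 (0.034 of 0.100).

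**6. Subjects whom section 11.2 does not reach.** The same formulas at p = 0.33:
- Stops after 21 days: 0.526 if lost then (p_t = 0.125), against 0.493 if observed to Day 35 (p_t = 0.199). Difference 0.033.
- Full course, lost at Day 49: 0.462 (p_t = 0.268), against 0.434 if observed to Day 63. Difference 0.028, all of it missing observation.

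**7. Vary how common such subjects are.** Let a share w of all counted subjects stop at Day 14, and put (1 − w)p + w·p_t in place of p in step 3. At p = 0.33 and w = 10%, 20%, 30%, P(escalate) is 0.48, 0.53, 0.59 if they are lost at Day 14, and 0.47, 0.50, 0.54 if they are observed to Day 28. The documents give no value for w.

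**The case against.** The strongest reply is that the protocol does not plan to lose these subjects. Section 10.2 expressly covers prematurely discontinued subjects to 28 days after the last dose. Section 11.1 follows everyone who discontinues for a listed reason, consent withdrawal included, for 30 days. Both periods outlast the 14-day window. Section 10.3.3 also uses withdrawal from the study in the sense of stopping drug because of an adverse event, so criterion 3 need not mean leaving observation. DLT item 6 already scores a treatment-related stop with three or more missed doses as a DLT. And section 11.2 would replace the Day-14 subject on whom the main calculation rests.

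Most of this stands. A reader might infer that the plan admits unobserved subjects to cohorts as a matter of course. The documents do not support that: unobserved subjects *can* enter, when planned follow-up fails. A reader might also take the whole rise from 0.434 to 0.544 as the cost of missing observation. That is wrong too, because most of it remains when the Day-14 subject is observed to the end of their own window.

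Three things survive:
- The follow-up in 10.2 and 11.1 is a duty to collect data, not a condition of evaluability. If it fails, for example after consent withdrawal, criterion 3 still counts the subject. Section 10.2 also narrows adverse event collection once new anti-cancer therapy starts, although possibly related and clinically significant events are still collected.
- DLT item 6 does not cover a withdrawal for reasons other than toxicity that is followed by an unseen event.
- Section 11.2 contradicts criterion 3 for 14 to 20 days of drug, with nothing to say which prevails, and does not touch subjects with 21 or more days.

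**Conclusion.** The point holds in this limited form: criterion 3 does not make evaluability depend on completing the follow-up that the protocol already plans, and any resulting error favours escalation.

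For one early stopper among the first three at a true DLT rate of 0.33, missing observation adds about 0.03 to the probability of escalating: 0.035 for a loss at Day 14, 0.033 at Day 21 and 0.028 at Day 49. The larger difference for the Day-14 subject, 0.110 against replacement, is mostly shortened exposure. All of these figures rest on the constant-hazard and independence assumptions. The documents supply neither a withdrawal rate nor DLT timing, so the size for the trial as a whole cannot be fixed.

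Appendix G is arithmetically right and needs no correction. The gap sits inside section 4.2, and sections 11.2 and 13.2.2 add two further rules that do not agree with it. It should be corrected because a single subject can decide a cohort and the change is small.

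**What to change.** In section 4.2 and the Synopsis, make criterion 3 conditional on observation, for example: withdrawn after at least 14 days of lenalidomide and observed without a DLT to 14 days after the last dose. A subject who then meets no criterion is replaced under the existing Synopsis rule.

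In the same amendment, reconcile 4.2 with 11.2 (replacement of anyone withdrawn before 21 days) and with 13.2.2 (five doses without a DLT), so that one evaluability definition tied to the DLT window applies throughout. Changing criterion 3 alone would leave the same unobserved subject evaluable under 13.2.2. Which minimum exposure should apply is for the sponsor to settle. The observation condition does not remove the shortened-exposure part: a Day-14 subject who is observed to Day 28 and still counted leaves the probability at 0.509.

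The cost is one clause in two places, aligned wording in 11.2 and 13.2.2, an occasional extra replacement, and a short wait for the window to close before the cohort decision.

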4.3 Dose Limiting Toxicity

DLT will be defined as any of the following adverse events that are not clearly unrelated to drug administration or treatment-emergent from lenalidomide and constitute a change from baseline irrespective of outcome. For the purpose of dose-escalation decisions and MTD determination, only DLTs that occur before 14 days after the last dose of lenalidomide administration will be taken into account.

1. Grade 3 or greater nausea, diarrhea, or vomiting despite the use of maximal medical intervention;
2. Grade 3 or greater acute GVHD despite the use of maximal medical intervention;
3. Any other clinically significant nonhematologic toxicity of grade 3 or greater considered not related to the underlying disease or intercurrent illness;
4. Grade 3 or greater neutropenia
5. Grade 4 thrombocytopenia or platelet count ≤ 50 thou/mm³ by day 28 of lenalidomide administration; or
6. Any treatment-related effect leading to a subject missing 3 or more doses of lenalidomide.

4.4 Study Duration and Dates

The subject recruitment period is approximately 36 months, starting last quarter 2015. The study duration encompasses the following:

- Screening period of up to 14 days (+/- 7) days from Day +60; and

- The CD34+ donor chimerism will be performed on days +60 and +90 (± 7 days) post-transplant until the CD34+ donor chimerism drops to $\leq 90\%$. If the CD34+ donor chimerism continues to be $> 90\%$ by day +90 (± 7 days) post-transplant the patient will be removed from the study;
- Treatment with lenalidomide will start within 10 days after detection of the CD34+ donor chimerism $\leq 90\%$ and be continued for 21 days in a 28-day cycle X 2 cycles or until terminating event occurs, whichever occurs first;
- In subjects receiving lenalidomide, the CD34+ donor chimerism will be performed at Days +60 and +120 (± 7 days) of lenalidomide therapy.

4.5 Correlative Studies

Peripheral blood will be collected to examine the CD34+ specific chimerism at the time-points as described in the Schedule of Events.

5. SELECTION OF SUBJECTS

5.1 Number of Subjects

It is anticipated that up to 24 allo-HCT recipients with AML and MDS will receive lenalidomide in this study. Justification for sample size is provided in Section 13.1. Subjects in this study can be of any race, gender and ethnic group.

5.2 Inclusion Criteria

- 1) Subjects must be at least 18 years of age;
- 2) Subjects must be 60 (+/- 7) days post-allogeneic transplant from any donor source;
- 3) Subjects must have either:
 - a) High risk CD34+ AML (*de novo* or secondary, and any WHO 2008 classification excluding acute promyelocytic leukemia, see Appendix A: AML WHO 2008 Classification System³). High risk AML is defined as (a) disease status beyond complete remission (CR) #1 at transplant or (b) treatment related AML or (c) presence of adverse cytogenetics including *inv(3)*; *t(3;3)*; *t(6;9)*; *t(v;11)*; -5 or *del(5q)*; -7; *abnl(17p)* or complex karyotype; or
 - b) High risk CD34+ MDS (WHO 2008 classification, see Appendix B: MDS WHO 2008 Classification System³⁴). High risk is defined as (a) blast count $\geq 5\%$ at the time of transplant or (b) treatment related MD or (c) presence of adverse cytogenetics including *-7/del7q* or complex karyotype;
- 4) For AML subjects, they must have a documented CR within 45 days prior to allo-HCT;
- 5) For MDS subjects, they must have $< 20\%$ myeloblasts in the bone marrow within 45 days prior to allo-HCT;
- 6) Subject Karnofsky performance status must be ≥ 70 (see Appendix E: Karnofsky Performance Status);
- 7) Subjects must be platelet transfusion independent (Platelet transfusion independence is defined as 7 days or greater without a platelet transfusion);
- 8) Neutrophil count ≥ 1.0 thou/mm³ and platelet count ≥ 30 thou/mm³;
- 9) Subjects must have total bilirubin ≤ 2 mg/dL;

- 10) Subjects must have serum AST and ALT levels ≤ 2.5 times upper limit of normal;
- 11) Subjects must have serum creatinine < 2.5 times upper limit of normal and a calculated creatinine clearance ≥ 30 ml/min by Cockcroft-Gault formula (see [Appendix I: Cockcroft-Gault Creatinine Clearance Calculation](#));
- 12) All study participants who will receive lenalidomide based on the CD34+ chimerism testing must be registered into the mandatory Revlimid REMS[®] program, and be willing and able to comply with the requirements of the REMS[®] program;
- 13) Females of child-bearing potential (*i.e.*, women who are pre-menopausal or not surgically sterile) may participate, provided they meet the following conditions:
 - a) Females of reproductive potential must adhere to the scheduled pregnancy testing as required in the Revlimid REMS[®] program; and
- 14) Written, voluntary informed consent, willingness, and ability to comply with all study procedures.

5.3 Exclusion criteria

- 1) CD34- AML or MDS;
- 2) Subjects with peripheral blasts or progressive cytopenias will be excluded unless a CR or CRi confirmed by a bone marrow biopsy within two weeks post of the allo-HCT;
- 3) Inability to give informed consent;
- 4) Uncontrolled active infection(s) requiring intravenous antibiotics;
- 5) Known or suspected hypersensitivity to lenalidomide;
- 6) Grade II-IV acute GVHD or extensive GVHD;
- 7) Not able to swallow the lenalidomide capsule as a whole; or
- 8) Female subjects who are pregnant or nursing.

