	
9. Subjects must have total bilirubin ≤ 2 mg/dL;
 
10. Subjects must have serum AST and ALT levels ≤ 2.5 times upper limit of normal;
 
11. Subjects must have serum creatinine < 2.5 times upper limit of normal and a calculated creatinine clearance ≥ 30 ml/min by Cockcroft-Gault formula (see Appendix I: Cockcroft-Gault Creatinine Clearance Calculation);
 
12. All study participants who will receive lenalidomide based on the CD34+ chimerism testing must be registered into the mandatory Revlimid REMS[®] program, and be willing and able to comply with the requirements of the REMS[®] program;
 
13. Females of child-bearing potential (i.e., women who are premenopausal or not surgically sterile) may participate, provided they meet the following conditions:
 
a) Females of reproductive potential must adhere to the scheduled pregnancy testing as required in the Revlimid REMS[®] program; and
 
14. Written, voluntary informed consent, willingness, and ability to comply with all study procedures.
 
Exclusion Criteria:
 
 1. CD34- AML or MDS; 2. Subjects with peripheral blasts or progressive cytopenias will be excluded unless a CR or CRi confirmed by a bone marrow biopsy within two weeks post of the allo-HCT; 3. Inability to give informed consent; 4. Uncontrolled active infection(s) requiring intravenous antibiotics; 5. Known or suspected hypersensitivity to lenalidomide; 6. Grade II-IV acute GVHD or extensive GVHD; 7. Not able to swallow the lenalidomide capsule as a whole; or 8. Female subjects who are pregnant or nursing;

Accrual:
	
The sample size for the study is based on incidence of DLT; however, it is not to exceed 24 subjects. The accrual period will be three years.

Study Duration and Dates:
	
The subject recruitment period is approximately 36 months, starting last quarter 2015. The study duration encompasses the following:
 
 • Screening period of up to 14 days (+/-7 days from Day +60); and • The CD34+ donor chimerism will be performed on days +60 and +90 (± 7 days) post-transplant until the CD34+ donor chimerism drops to $\leq 90\%$. If the CD34+ donor chimerism continues to be $> 90\%$ by day +90 (± 7 days) post-transplant the patient will be removed from the study; • Treatment with lenalidomide will start within 10 days after detection of the CD34+ donor chimerism $\leq 90\%$ and be continued

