Statistical Procedures:	This study is descriptive in nature and not designed to provide analytical inferential results regarding primary or secondary endpoints. The sample size is based primarily on clinical considerations and not on statistical power calculations. Statistical characteristics of the “3 + 3” design are described in Appendix G. Descriptive statistics will be used to summarize baseline subject characteristics, treatment administration, and safety variables. All subjects who receive at least 5 doses of lenalidomide and have one post-dose safety assessment will comprise the safety population. The efficacy evaluable population will comprise all subjects who complete

	at least 15 days of lenalidomide and have at least one post-therapy CD34+ specific chimerism assessment.
--	--

Schedule of Events

Assessment	Screening (+/-7 days from Day +60)	Post- Transplant Monitoring Days +60 & 90 (\pm 7 days)	Revlimid C1D1, C2D1	End of Treatment 30 Days post- last Revlimid Dose (\pm 2 days)	Post- Revlimid Monitoring Days +60 & +120 (\pm 7 days)	Survival Every 3-months for 1 year
Signed Informed Consent	X					
Demographics, Medical /Treatment History	X					
MDS and AML WHO Classification	X					
Weight, Height	X					
Physical Examination	X	X	X	X	X	
GVHD Assessment ^A	X	X	X	X	X	
Vital Signs	X	X	X	X	X	
Karnofsky Performance Score	X	X	X	X	X	
CBC + Differential	X	X	X	X	X	
Serum Chemistry	X	X	X	X	X	
Serum Pregnancy Test (females) ^B	X		X			
Bone Marrow Aspiration and Biopsy ^C	X					
Peripheral Blood Chimerism		X				
Peripheral blood CD34+ donor chimerism ^D		X			X	
Dispense Revlimid (21-day supply)			X			
Concomitant Medications	X	X	X	X		
Adverse Events Assessments	X	X	X	X		
Concomitant Blood Products	X	X	X	X		
Disease Response Assessment ^C	X	X				X
Survival Assessment				X		X

- A. Overall grading and response to GVHD therapy will be measured through the use of the consensus and IBMTR GVHD severity indices. GVHD assessments will be performed at screening and Days +60 & +90. If lenalidomide is initiated, GVHD assessments will be performed weekly during scheduled visits and continuing until 30 days after the last dose of lenalidomide. GVHD assessments will also be documented at Days +60, and Day +120 after the initiation of lenalidomide.

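### As worded, exclusion 2 excuses peripheral blasts or progressive cytopenias at entry on a marrow that is 39 to 67 days old; the time anchor is probably a drafting slip and needs correcting in both places

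*Combined protocol and SAP*

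**What the plan says.** Section 5.3, item 2, excludes subjects with peripheral blasts or progressive cytopenias "unless a CR or CRi confirmed by a bone marrow biopsy within two weeks post of the allo-HCT". The Synopsis has the same rule: "Subjects with peripheral blasts or progressive cytopenias will be excluded unless a CR or CRi confirmed by a bone marrow biopsy within two weeks", again counted from the transplant. Neither place ties the marrow to screening or to the onset of the findings.

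Section 5.2, item 2, fixes the time of entry: "Subjects must be 60 (+/- 7) days post-allogeneic transplant from any donor source".

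The other disease-status criteria look back before transplant. AML subjects qualify if "they must have a documented CR within 45 days prior to allo-HCT" (item 4). For MDS, item 5 sets a ceiling on "myeloblasts in the bone marrow within 45 days prior to allo-HCT".

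The Schedule of Events marks "Bone Marrow Aspiration and Biopsy" at Screening, and "Disease Response Assessment" at Screening and at Days +60 and +90. Both rows carry footnote C, which leaves marrow procedures and other disease assessments to local guidelines or the physician's judgement. "CBC + Differential" is marked at Screening, at Days +60 and +90, and on day 1 of each cycle. Section 8.1 says that all subjects have the procedures in the Schedule.

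**The concern.** The exception exists to separate blasts or falling counts that are compatible with remission from those that are relapse, and it relies on a marrow to do so. For that, the marrow must speak to the subject's condition when the findings are seen. A marrow dated by the transplant, in a trial that enrols about two months later, does not.

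The rationale in the Synopsis is to treat minimal residual disease before relapse shows itself clinically, while tumor burden is low. A subject already in hematologic relapse falls outside that population. If such a subject were treated, the efficacy outcome (recovery of CD34+ donor chimerism by day 60 of lenalidomide) would be described in a mixed group.

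**Working it through.** The plan states no age for the qualifying marrow, so there is no figure to reproduce. The check is interval arithmetic.

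**Inputs**
- Entry day (section 5.2, item 2): 60 − 7 = +53 to 60 + 7 = +67.
- Qualifying marrow (section 5.3, item 2, read literally): day 0 to day +14.
- Date of the findings: exclusion 2 gives none. I assume that it refers to status at screening and entry.

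**Age of the marrow = entry day − marrow day**

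| Marrow taken | Entry on day +53 | Entry on day +67 |
|---|---|---|
| Day +14 | 53 − 14 = 39 days | 67 − 14 = 53 days |
| Day 0 | 53 − 0 = 53 days | 67 − 0 = 67 days |

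The full range is 39 to 67 days. Even the newest qualifying marrow is at least 39 days old.

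**Comparison, on an assumption.** Suppose that the two weeks were meant to run back from entry. The marrow would then fall between day 53 − 14 = +39 and day +67, and would be 0 to 14 days old. The latest marrow allowed by the literal text (day +14) comes 39 − 14 = 25 days before the earliest one allowed by this reading (day +39). No marrow satisfies both, so the choice of reading decides who may use the exception.

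**Does anything else check marrow status at entry?**
- Inclusions 4 and 5 concern status before transplant.
- Inclusions 7 and 8 (platelet transfusion independence, neutrophils ≥ 1.0 and platelets ≥ 30 thou/mm³) and section 6.2 (ANC ≥ 1.0, platelets ≥ 50 thou/mm³, chimerism ≤ 90%) set floors on counts and a chimerism threshold. None sets a condition on blasts, trend or marrow.
- CBC differentials can reveal blasts or falling counts, but these are the findings that the exception excuses.
- The Screening marrow is scheduled, but footnote C qualifies it and no criterion requires its result.
- Footnote D and section 9.1.2 provide for extra CD34+ chimerism testing at the investigator's discretion, for example when blasts or worsening pancytopenia develop. It is not a condition of entry.
- Section 11.1 requires therapy to stop for relapsed or progressive disease, or if the Principal Investigator thinks that continuing could harm the subject. It governs discontinuation, not entry.

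**Reach into the results.** Section 5.1 expects up to 24 subjects to receive lenalidomide, so one subject is at least 1/24 = 4.2 percentage points of the overall chimerism proportion if counted. Who is counted is unsettled: the Synopsis (Statistical Procedures) requires at least 15 days of drug, and section 13.2.3 requires at least 21.

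**The case against.** The strongest reply is that this is a slip of the pen. The phrase is ungrammatical. The Synopsis and section 4.4 describe a screening period of up to 14 days around Day +60, which matches the two weeks in the exclusion. The Schedule marks a marrow at Screening, and section 8.1 applies the Schedule to everyone. Together these suggest that a post-transplant marrow close to entry was meant. Footnote C can also be read as governing how or when the marrow is done, not whether.

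Most of this stands, and I think a slip is the likelier explanation. It remains an inference: the text states another anchor, in two places, and no criterion asks for the Screening result. On either reading the same phrase has to be changed.

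The protections listed above also stand in part. They lower the chance that a relapsed subject is treated for long. None establishes marrow status at entry.

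Four stronger readings are tempting but not supported:
- A reader might infer that the sponsor chose to accept an old marrow. Nothing in the plan argues for that, and the Schedule points the other way.
- A reader might infer that anyone using the exception is in relapse, or that relapsed subjects would go unnoticed. Blasts or cytopenias are not in themselves relapse. Section 11.1 also allows for stopping on grounds of possible detriment, before relapse is established.
- A reader might infer a distortion of the DLT counts or of dose escalation. The documents do not show how often the exception would be used or how such a subject's events would be attributed, so no such effect is claimed.
- A reader might quote larger ages, such as marrow age at first dose or the age of the pre-transplant evidence. Exclusion 2 is applied at entry, and inclusions 4 and 5 are not part of its exception, so 39 to 67 days is the relevant figure.

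**Conclusion.** The point holds as an eligibility rule that is wrong as written. Followed literally, exclusion 2 excuses current blasts or progressive cytopenias on a marrow 39 to 67 days old at entry (39 to 53 days if taken on day +14), which cannot show whether those findings are relapse. A subject already in relapse could therefore enter and blur the descriptive chimerism outcome.

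This rests on two assumptions: the literal reading of the anchor, and findings judged at screening and entry. If the two weeks were meant to run back from entry, the marrow would be 0 to 14 days old and only the wording would be at fault.

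Severity is low to moderate. The rule is probably a slip, partial protections exist, the outcome concerned is secondary and descriptive, and the number of subjects who would use the exception is unknown.

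**What to change.** The sponsor should correct the time anchor of exclusion 2 in section 5.3 and in the Synopsis, so that it is reconciled with the day +60 entry window and with the population described in the rationale. The sponsor should also state how footnote C applies to the Screening marrow for subjects who use the exception. The clinical rule and the length of the window are for the sponsor to set; none is proposed here.

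The cost is one phrase in two places and one clarifying statement. A marrow is already in the Screening column, so whether any subject needs a further procedure depends on the rule chosen. The downside is that a subject with blasts or progressive cytopenias and no such marrow could not use the exception.

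The 15-day and 21-day definitions of the efficacy population also need to be reconciled, because they decide whether such a subject counts in the chimerism outcome.
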